2.2 Study Comparators (SC-1)

In its original certification process and its periodic recertification of clinics as Health Care Homes (HCH), MDH conducts both a written and a site visit-based evaluation to verify that every HCH clinic has implemented required standards or has obtained a variance if a particular subpart is not possible at that time. The relevant MDH standards (MN Administrative Rule #4764.0040) require that a HCH must address each of the following subparts related to care coordination:

- 1A Systematically screens patients to identify those who would benefit from care coordination
- 5A Collaboratively develops patient-centered goals, identifies resources to achieve goals, ensures consistency and continuity of care, including frequency of follow-up.
- 5B Designates one clinician for each patient and one care coordinator as the primary contact
- 5C Ensures that the clinician and care coordinator communicate with each other directly
- 5D Ensures the care coordinator has dedicated time to perform coordination responsibilities
- 6B Identifies and works with community-based organizations to facilitate the availability of appropriate resources for patients
- Establishes and implements policies and procedures that guide who would most benefit from a care plan and develops the plan for identified individuals in a way that engages patient and team, incorporates risk assessment, is updated, and is provided to the patient

It is from this information that we have developed this definition to distinguish the two care model comparators below. Final classification of clinics to one of each comparator model will be determined from data collected through a survey of care coordinators in participating clinics.

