2.2.1 Care coordination model comparator definitions

Clinics meeting all four of the following criteria are classified as using a **Medical/Social** model of care coordination:

1. At least one social worker (licensed or not) is part of the care team at the clinic, and
2. The social worker is responsible for assessing and coordinating social services for care coordination patients at the clinic, and
3. The social worker routinely interacts with clinicians at that clinic, and
4. The social worker routinely interacts with care coordinated patients.

Clinics that do not satisfy every part of this definition are classified as using a **Medical/Nursing** model of care coordination.

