2.2.2 Measuring Fidelity and Model Components

In order to answer the main research question in Aim 1, it is crucial to have accurate knowledge about the type of care model present in each study clinic at the time the Primary Cohort began care coordination. It is also important to know how that model has changed since 2018 when the Historical Cohort was beginning to receive care coordination, during the pandemic in 2020, and whether any changes are planned during the post-coordination year for the Primary Cohort. Therefore, we will

employ the three strategies in **Table 1** to ascertain and confirm both the overall model used, and the core functions/components of care coordination delivery at each clinic throughout this time. These data will allow us to characterize both fidelity to the overall model and the specific ways in which there is variation within and between both models at the level of individual clinics. Timing of the patient cohorts and data collection efforts is illustrated in **Figure 1**.

Table 1: Strategies for Measuring and Accounting for Fidelity to Each Care Coordination Model

Strategy	Description	Sample Size	Expected Response Rate	Timeframe
1	Care Coordinator Survey	~300-400	100% (required)	Q1 2022
2	Organizational Survey	~50-70	100% (required)	Q3 2021
3	Primary Cohort Patient Survey	~7,000 (~20/clinic)	60%	Q3 2022

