The primary strategy will involve requiring the lead care coordinator at each participating clinic to complete a survey that asks about each core component. This survey will be conducted in the fall of 2021, at a time when the clinics will have renormalized as COVID-19 pressures have declined. This timing will align with the Primary Cohort identification period (1/21-12/21), so it will provide a very specific verification of implementation models during the time the Primary cohort was being enrolled and receiving services. The response rate for this survey will be 100% because completing the survey is a requirement of participation in the study, which we have communicated to clinics throughout our recruitment process. We shall also ask the lead care coordinators whether any of these core components have changed in any significant way during the preceding 3 years (with a focus on 2018 to correspond with the Historical cohort) and whether they are expected to change in the next year. These surveys will be preceded by semi-structured interviews with about 20 care coordinators for the purpose of identifying every potentially important component of care coordination needed to be included in the survey. The study team will design the care coordination survey to measure these components, using existing and validated assessment tools wherever possible. We will draw upon measurement tools and definitions identified or endorsed by the Agency for Healthcare Research Quality (AHRQ) and National Quality Forum (NQF).²⁸⁻³² We will also rely on the expertise of our external consultants [name] (lead author of the 2014 update of the AHRQ Care Coordination Measures Atlas²⁸) and [name] (previously, Vice President for Research & Analysis, National Committee for Quality Assurance) to translate existing measures and develop supplemental measures as needed.

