- housing/transportation/food needs assessment and referrals
- mental health or emotional needs assessment and referrals
- patient education and health behavior counseling
- spiritual needs assessment and referrals
- transitional service needs (e.g. transitions in care or placement needs)
- referrals for other community resources
- other (please explain) _____ [services_other]

Is any “tiering” or complexity tool used to assess the level of care coordination needed for individual patients? [tiering]

- yes, for all patients
- yes, but only for some patients
- no

How many of the certified HCH clinics in your medical group currently have a social worker with dedicated time for care coordination activities at that clinic? *By social worker we mean someone with an educational degree in social work. This individual does not need to be a licensed social worker.* [clinicSW]

C: Please answer the following questions about social workers with dedicated time for care coordination activities:

[If more than one clinic in the organization clinicSW >1], On average, how many clinics is each social worker assigned to? [SWcount] _____

[If one or more >=1 here and for rest of section], Does the social worker normally interact with individual patients to provide them with care coordination services? [SWpatient]

yes
 no

Does the social worker normally interact with individual clinicians about their individual patients? [SWclinician]

yes → If yes, are these interactions regularly scheduled or ad hoc?
[swclinician_yes]
 no, social worker only provides general information about community resources or how to handle specific types of patient problems

Does the social worker normally work on site at each assigned clinic at least 1 day/week? [SWonsite]

yes, for all assigned clinics
 for some, but not all assigned clinics
 no

Does your medical group bill any of the following payment sources for care coordination services? (Please check all that apply). [paymentsources]

Medicare
 Medicaid/Medical Assistance/PMAP/MinnesotaCare
 commercial insurance
 specific ACO encounters/visits
 patients (without insurance or out-of-pocket)
 none
 other (please explain) _____ [paymentsources_other]

Does your medical group participate in any Value Based/Risk Based contracts or Accountable Care Organization agreements that include financial incentives for care coordination specifically? [ValueACO]

Yes → If yes, (what % of your care coordination patients are in this category)?

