11. Is there at least one person with a social worker degree (licensed or not) who is considered part of the care team at [clinic name] and works on site at least some of the time? [sw_team]

- 1, Yes
- 0, No

[if reporting for more than 1 clinic] Ask question for each specific clinic

[If Yes to Q11] 11a. Is the social worker a care coordinator (that is, do they have a personal panel of adult care coordination patients they are assigned to provide coordination services to over time)? [sw_cc]

- 1, Yes
- 0, No

[If Yes to Q11] 11b. How many social workers are considered part of the care team at [clinic name]? [sw_team_num]

- 1, 1
- 2, 2
- 3, 3 or more

[if reporting for more than 1 clinic] Ask question for each specific clinic

[If Yes to Q11] 11c. Are they responsible for assessing and coordinating social services for care coordination patients at [clinic name]? [sw_responsible]

- 2, Yes, for all patients in care coordination
- 1, Yes, but only for those patients that are referred to the social worker because of need for social services
- 0, No

[if reporting for more than 1 clinic] Ask question for each specific clinic

[If Yes to Q11] 11d. Do they regularly interact with care coordination patients? [sw_interact]

- 1, Yes
- 0, No

[If yes, interact w patients] 11da. Who usually initiates interactions between the social worker and the patient? [sw_initiate]

- 1, Most often the social worker
- 2, About equal
- 3, Most often the patient

[If yes, interact w patients] 11db. About how often are each of the following forms of communication used for the social worker and patient interaction? [sw_com]

[Always used, mostly used, sometimes used, rarely used, never used]

4 3 2 1 0

In-person meeting [sw_com_meet]

Telephone [sw_com_phone]

Video call [sw_com_video]

Message through EMR [sw_com_emr]

Some other, [sw_com_oth] Please specify: _____ [sw_com_other]

[If yes, interact w patients] 11dc. On average, how many interactions does the social worker have each month with patients receiving ongoing care coordination?

[sw_interact_num]

0, Less than once per month

1, 1

2, 2

3, 3

4, 4 or more

[If Yes to Q11] 11e. Does the social worker routinely interact with clinicians of care coordinated patients regarding their care? [sw_interact_clinician]

1, Yes

0, No

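### The survey item that opens the clinic classification adds an on-site condition absent from the Medical/Social definition and is not tied to 2021, so some clinics can be put in the wrong group

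*Combined protocol and SAP*

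**What the plan says.** **The definition.** Section 2.2.1 lists four criteria for a Medical/Social clinic. The first is: "At least one social worker (licensed or not) is part of the care team at the clinic". The others concern responsibility for social services, routine contact with clinicians, and routine contact with patients. None mentions working on site. Failing any one is decisive: "Clinics that do not satisfy every part of this definition are classified as using a" Medical/Nursing model.

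**The instrument.** Section 2.2 says: "Final classification of clinics to one of each comparator model will be determined from data collected through a survey of care coordinators". In Appendix F, item 11 asks in the present tense whether there is a person with a social work degree "who is considered part of the care team at [clinic name] and works on site at least some of the time". It takes a yes or a no. Items 11c, 11d and 11e, which correspond to the other three criteria, are asked only after a yes.

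**The reference period.** Section 2.2.2 says that Aim 1 needs accurate knowledge of "the type of care model present in each study clinic at the time the Primary Cohort began care coordination", that is, January to December 2021. On fielding, the text of 2.2.2 says "This survey will be conducted in the fall of 2021", Table 1 in the same section says Q1 2022, and the milestones in Section 10 give April 15, 2022 as the expected completion date.

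**The concern.** The written rule and the instrument that applies it define different exposures.

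- **On-site condition.** A clinic served by a wholly remote social worker can meet all four criteria in 2.2.1, yet its coordinator must answer no to item 11. Items 11c to 11e are then skipped, so the survey holds nothing from which the clinic could be reclassified.
- **Timing.** Item 11 records the model on the day of the survey. The other period items in Appendix F cover the time before about March 2020 (item 12) and plans for the rest of the current year (12c, 13a). No item asks about the social worker during 2021.

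The classification enters every Aim 1 model for the Primary Cohort as the exposure term. Misplaced clinics would mix the two groups and, in the simplest case, draw the estimated differences toward zero. Section 9.1.2 treats the exposure as never missing, and no analysis of exposure misclassification is specified. The E-values in 7.3.6.1 address unmeasured confounding, and the bias analyses in 7.3.8 are described only in general terms.

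**Working it through.** **1. Definition against instrument**

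| 2.2.1 criterion | Appendix F item | Difference |
|---|---|---|
| Social worker on the care team | 11 | Item adds on-site work |
| Responsible for social services | 11c, only after yes to 11 | Three answer options; no rule says whether covering referred patients only is enough |
| Interacts with clinicians | 11e, only after yes to 11 | Filter only |
| Interacts with patients | 11d, only after yes to 11 | Filter only |

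**2. Date.** Item 3 of Appendix F asks about 2021 in the past tense, which fits fielding in 2022. Even in fall 2021, a present-tense answer would not describe a clinic that changed model earlier that year.

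**3. The plan's own figure.** Section 7.2.1 gives 397 clinics split 55/45, two-sided alpha 0.05, 80% power, ICC 0.01, a PROMIS-10 SD of 10, and 7,000 × 60% = 4,200 survey responses. With m responses per clinic:

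SE = 10 × √{[1 + (m − 1) × 0.01] × (1/n₁ + 1/n₂)}; detectable difference = (1.960 + 0.842) × SE.

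Here n₁ = 0.55 × 4,200 = 2,310 and n₂ = 0.45 × 4,200 = 1,890. All clinics recruited (m = 10.6) gives 0.91 points; 75% recruited (m = 14.1) gives 0.92. The plan's 1-point statement reproduces for both planned survey scenarios.

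**4. On-site error alone (one-way).** Let a share q of true Medical/Social clinics be coded Medical/Nursing. The coded Medical/Social group stays pure, while the coded Medical/Nursing group contains a fraction 0.45q/(0.55 + 0.45q) of true Medical/Social clinics. The observed difference shrinks by that fraction:

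- q = 5%: 0.0225/0.5725 = 3.9%
- q = 10%: 0.045/0.595 = 7.6%
- q = 20%: 0.09/0.64 = 14.1%

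The next table recomputes the SE at the coded split. Clinics moved = 397 × 0.45 × q. Paired figures are for 100% / 75% of clinics recruited.

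| q | Clinics moved (of 179) | Power for a true 1-point difference | Detectable true difference |
|---|---|---|---|
| 0 | 0 | 86.9% / 85.8% | 0.91 / 0.92 |
| 5% | 9 | 83.7% / 82.5% | 0.95 / 0.97 |
| 10% | 18 | 80.2% / 79.0% | 1.00 / 1.01 |
| 20% | 36 | 72.4% / 71.0% | 1.10 / 1.12 |

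**5. Error in both directions, as timing can cause.** Let a share r of true Medical/Nursing clinics also be coded Medical/Social. The coded Medical/Social share is c = 0.45(1 − q) + 0.55r, and the observed difference is the true one times 0.45(1 − q)/c − 0.45q/(1 − c).

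- q = r = 5%: 0.4275/0.455 − 0.0225/0.545 = 0.898; power 79.1% / 77.8%.
- q = r = 10%: 0.405/0.46 − 0.045/0.54 = 0.797; power 69.1% / 67.8%.

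q and r are assumptions throughout; the documents give neither. The formulas describe differences in means without covariates, so for odds and rate ratios they are only a guide.

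**The case against.** **The on-site wording may be deliberate.** Section 2.2.1 speaks of the team at the clinic, and the same minimal on-site phrase recurs in items 11, 12, 12c and 13a. If occasional presence belongs to the intended model, no clinic is misplaced on this ground. That may be so, but 2.2.1 does not say it, and Appendix D treats on-site work as a question of its own. The two texts still have to be made to agree.

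**There are other checks.** The organizational survey, due in fall 2021, asks about current social workers and their contact with patients and clinicians. Item 14 of the Primary Cohort survey (Appendix H) asks about help from a clinic social worker since coordination began. Section 2.2.2 plans follow-up with clinic staff where patient answers diverge from the assigned model. A reader might infer that nothing in the study bears on 2021; that holds only within Appendix F. These checks are partial, however. The organizational item on clinics with a social worker is a count per medical group, so outside one-clinic groups it cannot name a clinic. The follow-up has no trigger and no reclassification rule.

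**No affected clinic is shown.** A reader might infer that the study expects remote-only clinics, because item 11db lists phone, video and record messaging and Appendix D allows a no to on-site work. Neither supports this. Item 11db is reached only after a yes to item 11. Appendix D asks "Does the social worker normally work on site at each assigned clinic at least 1 day/week", so a social worker present twice a month is a no there and a yes to item 11. This part of the objection stands in full.

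**Conclusion.** The mismatch is on the page: the item that opens the classification carries a condition that the definition lacks, and its filter prevents correction from the same survey. The reference period is also unsettled, because the fielding dates conflict and the item asks about the present.

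Two stronger readings are not supported. One is that qualifying clinics are in fact coded wrongly: no scoring rule is written and no count of affected clinics is given, so the text supports only that they can be. The other is that all the error runs one way. That is true of the on-site wording, but a clinic that adds a social worker after its 2021 patients enrolled would be coded Medical/Social, so timing error runs both ways.

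The size is conditional. A 3.9%, 7.6% or 14.1% shrinkage follows if the on-site wording alone misplaces 5%, 10% or 20% of true Medical/Social clinics, at a true 55/45 split, with clinics of equal size and remote-only service having the full Medical/Social effect. If remote service has a smaller effect, the loss is smaller. At 10% the planned power for a 1-point PROMIS-10 difference is still about 80%. The matter deserves correction because it concerns the exposure itself and the remedy is cheap.

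**What to change.** 1. Reconcile the survey date across the text of 2.2.2, Table 1 and Section 10.
2. Make definition and instrument agree. If the survey is still open, let team membership alone lead to 11c to 11e, record on-site work as a separate item, and word the items for 2021. If fielding is complete, which the past-tense wording of Appendices A and B and the April 2022 milestone suggest, state the on-site condition in 2.2.1.
3. Write the scoring rule from items 11 to 11e to the exposure, including how the three answers to 11c count.
4. Flag doubtful clinics for the staff follow-up already planned in 2.2.2. Compare each medical group's organizational count with the number of its clinics answering yes to item 11, and compare the assigned model with patient answers to item 14 of Appendix H.
5. Add a sensitivity analysis that reclassifies or excludes clinics whose class is doubtful because of on-site status or a change of model.

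The cost is a small instrument edit or limited follow-up, plus one extra analysis. Follow-up has limits: coordinators would be recalling 2021, and in multi-clinic groups the count narrows the search without identifying the clinic.

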[If yes, interact w clinicians] 11ee. Which of the following forms of communication are used for the social worker and clinician interaction at [clinic name]? Check all that apply. [sw_communicate_clin]

- 1, In-person meeting
- 2, Ad hoc in-person conversation
- 3, Telephone
- 4, Video call
- 5, Message through EMR
- 99, Some other, Please specify: _____ [sw_communicate_oth]

[if reporting for more than 1 clinic] Ask question for each specific clinic

[If Yes to Q11] 11f. How easy or difficult is it for you to engage help from the social worker when needed? [sw_engage]

4, Very easy

3, Somewhat easy

2, Somewhat difficult

1, Very difficult

99, N/A (I am the social worker)

[Page break]

12. Before the onset of the COVID-19 pandemic was there at least one person with a social worker degree (licensed or not) who was considered part of the care team at [clinic name] and worked on site at least some of the time? [before_covid_sw]

1, Yes

0, No

99, Not sure

[if reporting for more than 1 clinic] Ask question for each specific clinic

[If yes to Q12] 12a. Did they regularly interact with care coordination patients?
[covid_sw_interact_pat]

1, Yes

0, No

99, Not sure

[if reporting for more than 1 clinic] Ask question for each specific clinic

[If yes to Q12] 12b. Did they routinely interact with clinicians of care coordinated patients regarding their care? [covid_sw_interact_clin]

1, Yes

0, No

99, Not sure

[if reporting for more than 1 clinic] Ask question for each specific clinic

[if yes to Q12] 12c. Does [clinic name] plan to continue to have a social worker (licensed or not) that is on site at least some of the time and part of the care team for the remainder of this year? [covid_sw_plan]

1, Yes

0, No

99, Not sure

[if reporting for more than 1 clinic] Ask question for each specific clinic

[If yes] 12ca. Would they regularly interact with care coordination patients? [plan_interact_pat]

1, Yes

0, No

99, Not sure

[if reporting for more than 1 clinic] Ask question for each specific clinic

[If yes] 12cb. Would they routinely interact with clinicians of care coordinated patients regarding their care? [plan_interact_clin]

1, Yes
0, No
99, Not sure

[if reporting for more than 1 clinic] Ask question for each specific clinic

[if no or not sure to Q12] 13a. Is there any plan to add a person with a social worker degree (licensed or not) who would be on site at least some of the time to the care team at [clinic name] yet this year? [plan_add_sw]

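### Survey item 11d, which supplies criterion 4 of the Medical/Social definition, is printed without the per-clinic repeat, and item 11e (criterion 3) is ambiguous, so clinics sharing a respondent can be put in the wrong arm

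*Combined protocol and SAP*

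**What the plan says.** Section 2.2 makes the care coordinator survey the source of the exposure: "Final classification of clinics to one of each comparator model will be determined from data collected through a survey of care coordinators". Section 2.2.1 lists four criteria that must all hold. The third is tied to the clinic, "The social worker routinely interacts with clinicians at that clinic, and", and the fourth reads "The social worker routinely interacts with care coordinated patients". Failure on any one decides the arm: "Clinics that do not satisfy every part of this definition are classified as using a Medical/Nursing model of care coordination".

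Appendix F allows one respondent to report for more than one clinic and marks the items to be repeated in that case. Items 11, 11b and 11c carry the mark and name the clinic. The item for criterion 4 is printed as "11d. Do they regularly interact with care coordination patients? [sw_interact", with no clinic name and no repeat, and its sub-items 11da to 11dc have no repeat either. The item for criterion 3 is "11e. Does the social worker routinely interact with clinicians of care coordinated patients regarding their care? [sw_interact_clinician". It also has no clinic name and no repeat of its own. The next repeat instruction follows 11ee, which does name the clinic. The pre-COVID counterpart of 11d, "12a. Did they regularly interact with care coordination patients", has its own repeat instruction.

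**The concern.** The Aim 1 comparison is a clinic-level exposure in every model (the CC term in equation 1, Section 7.3.1), and Section 2.2.2 treats accurate knowledge of each clinic's model as essential. One of the four items that decide the exposure appears to be collected per respondent when it should be collected per clinic, and a second may be. A coordinator who covers two clinics, both with a responsible on-site social worker but with real contact between that person and patients at only one, has no place to record the difference. Section 9.1.2 says the exposure will not be missing and gives no rule for spreading one answer over several clinics. Applying it to all of them is the natural outcome.

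Two things are at stake. Misclassified clinics dilute the Aim 1 contrast. In addition, the current item would be coarser than its pre-COVID counterpart, so an apparent change of model at a clinic could come from the questionnaire.

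**Working it through.** The plan states no figure on this point. The check is a reading of the items against the criteria, followed by an illustration of scale.

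**Items against criteria**

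| Criterion (Section 2.2.1) | Current item | Names the clinic | Per-clinic repeat |
|---|---|---|---|
| 1. Social worker on the team | 11 | yes | yes |
| 2. Responsible for social services | 11c | yes | yes |
| 3. Interacts with clinicians | 11e | no | none of its own; next one after 11ee |
| 4. Interacts with patients | 11d | no | none, nor after 11da to 11dc |

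The matching patient-contact items for the pre-COVID period (12a), for continuation (12ca) and for a planned addition (12aa) each have their own repeat. So do the clinician-contact items 12b, 12cb and 12ab. Only the current-model versions lack it.

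**When an error arises.** Suppose a respondent covers clinics A and B, both are Yes at 11 and 11c, and A truly meets criterion 4 while B does not. A single Yes to 11d makes both Medical/Social, and B is wrong. A single No makes both Medical/Nursing, and A is wrong. If B is instead No at 11 or 11c, B is Medical/Nursing whatever is entered at 11d. An error therefore needs clinics that share a respondent, pass 11 and 11c, and truly differ on criterion 4 (or on criterion 3, if 11e was also asked once).

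**Other sources.** The organizational survey (Appendix D) asks about social worker contact with patients and with clinicians once per medical group, so it cannot fill the gap. Item 14 of the Primary Cohort patient survey asks whether the patient received help from a social worker. That bears on criterion 4 but not on criterion 3, and Section 7.2.1 expects only about 10 to 14 responders per clinic.

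**Illustration of scale.** Inputs from Section 7.2.1 are 397 clinics split 45% medical/social and 55% nursing/medical, 10 responders per clinic, SD 10, intra-cluster correlation 0.01, two-sided alpha 0.05, 80% power, and a true difference of 1 PROMIS point.

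- Design effect = 1 + (10 − 1) × 0.01 = 1.09.
- Patients = 397 × 10 = 3,970, or 1,786.5 and 2,183.5 by arm.
- Minimum detectable difference = (1.960 + 0.842) × 10 × √[1.09 × (1/1,786.5 + 1/2,183.5)] = 0.93 points. Power for 1 point is 85%.

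Let q be the share of clinics labelled medical/social that are truly nursing/medical, and r the reverse share. The observed difference is then (1 − q − r) times the true one. The documents give neither q nor r, so their sum is an assumption:

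| q + r | Share of true effect seen | Minimum detectable true difference | Power for 1 point |
|---|---|---|---|
| 0 | 1.00 | 0.93 | 85% |
| 5% | 0.95 | 0.93/0.95 = 0.98 | 81% |
| 10% | 0.90 | 0.93/0.90 = 1.04 | 77% |
| 20% | 0.80 | 0.93/0.80 = 1.17 | 67% |

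**The case against.** The strongest reply is that Appendix F is a loosely annotated text version of a web form, so a missing mark does not prove that an item was asked once. Items 1 and 5 are plainly about a named clinic and carry no repeat mark. Item 24 has two lettered parts, both naming the clinic, with a single mark after the second. On that pattern the mark after 11ee could cover 11e as well, particularly since 11ee is shown only to those who answer Yes at 11e. Section 5.5.4 also pursues respondents until there is a completed survey for every clinic. This stands for 11e, and it is why that item is called ambiguous here. It is weaker for 11d, which has no mark on itself or its sub-items and does not name the clinic.

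A reader might infer that clinics under one coordinator are forced into the same arm. They are not: items 11 and 11c are asked per clinic, and a No on either settles that clinic's arm. Those two items would also screen out many pairs of a main clinic and a satellite.

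Section 2.2.2 promises follow-up with clinic staff where patient reports diverge from the designated model. That is a partial safeguard. It states no threshold for divergence, and it does not measure contact between social worker and clinicians.

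Finally, the form has probably been used already. Section 10 expected the survey by April 15, 2022 and the final Primary Cohort dataset by November 1, 2023, and the reference list shows pages accessed on December 19, 2023. This limits the remedy but does not remove the problem.

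**Conclusion.** The point holds for 11d as printed, and conditionally for 11e. If the form was fielded as printed, some clinics that share a respondent can be labelled wrongly, in either direction, on the variable that defines Aim 1. Whether that happened depends on the actual routing and on how a single answer was carried to several clinics; the documents state neither.

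The size is unknown. The documents do not say how many clinics share a respondent, how many of those pass 11 and 11c, or how many of those truly differ on criteria 3 or 4. It is tempting to read the illustration as an expected loss of 5% to 20% of the effect. The documents do not support that: an error share of 10% across all clinics would mean about 0.10 × 397 ≈ 40 misclassified clinics, and only the narrow group described above can contribute. The table shows what would follow from a given error share and does not estimate that share. It also assumes that errors are unrelated to outcome.

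The point is worth acting on because the exposure enters every Aim 1 model and the check is inexpensive. Sections 7.3.6, 7.3.8 and 9.1, which cover confounding, survey selection and missing data, do not name exposure misclassification.

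**What to change.** Add the clinic name and the per-clinic repeat to 11d and 11e, matching 11 and 11c.

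If the survey has already been fielded:

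1. Check in the fielded form how 11d and 11e were routed for respondents covering more than one clinic, and state this in the protocol. If both were repeated per clinic, correct the appendix and the point is closed.
2. If either was asked once, report how many clinics share a respondent, by arm, and how a single answer was assigned to them.
3. Re-ask the two yes/no items, clinic by clinic, of multi-clinic respondents who answered Yes at 11 and 11c for at least two clinics. Refer the questions to 2021 practice, and keep those who re-ask and reclassify unaware of clinic outcomes.
4. Add an Aim 1 sensitivity analysis that excludes, or reclassifies from the new answers, the clinics that share a respondent, and report it beside the main result.

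The cost is a slightly longer survey for multi-clinic coordinators or a short follow-up through the existing liaisons, plus one further analysis. Late re-asking brings some recall error, and excluding clinics lowers precision. Reclassification before outcome data are linked is probably no longer possible, which makes the sensitivity analysis the most dependable step.
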